### 2.2.3 Exploratory Efficacy Endpoints

The exploratory efficacy endpoints include:

- Change from baseline in quantitative SARS-CoV-2 viral load by nucleic acid amplification technology (NAT) or polymerase chain reaction (PCR; real-time reverse transcriptase [RT]-PCR) to Day 5± 1, Day 15± 1, and Day 29± 1
- Change from baseline in quantitative anti- SARS-CoV-2 immunoglobulin M (IgM) and IgG antibodies to Day 5± 1, Day 15± 1, and Day 29± 1
- Proportion of subjects with evidence of hyperinflammation on Day 1, Day 5, Day 15, and Day 29 defined as:
  - Lymphocyte counts <1000 cells/µL, AND
  - Two of the following 4 criteria:
    - Ferritin > 500ng/mL,
    - LDH > 300 U/L,
    - D-Dimers > 1000 ng/mL (fibrinogen equivalent units [FEU]) or > 2 times upper normal limit,
    - C-reactive protein (CRP) > 70 mg/L
- Change from baseline in cytokine profile (cytokine panel includes interleukin (IL)-1 $\beta$ , IL-10, IL-6, IL-8 IL-2, interferon  $\gamma$ , and tumor necrosis factor- $\alpha$  [TNF- $\alpha$ ]) to Day 5± 1, Day 15± 1, and Day 29± 1
- Change from baseline in levels of alpha 1-PI (AAT) activity and antigen through Day 29 (both plasma [sodium citrate] and serum samples to be stored for measurement of both antigenic content and functional activity [potency])

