#### 4.4 Handling of Dropouts or Missing Data

Missing data will be treated as missing and no method for imputation is planned for study population or safety analyses except for the partial end dates/times for concomitant medications (Section 5.6) and partial onset dates/times for AEs (Section 7.2.1). When applicable, missing data for binary and selected continuous efficacy endpoints will be imputed using a most conservative/worst case approach, and the related details are described in Section 6.

Time to event endpoints will have events coded as right censored or competing events per the following table:

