### 6.1 Primary Efficacy Endpoint and Analysis

The primary efficacy analysis will be carried out on the ITT population. If there is difference between the PP population and ITT population, the analysis will be repeated using the PP population.

The primary efficacy variable is the proportion of subjects who die or require ICU admission on

or before Day 29, or who are dependent on high flow oxygen devices or invasive mechanical ventilation on Day 29. The primary efficacy endpoint will be derived based on the subject status (Alive/Death), ICU admission, mechanical ventilation and oxygen administration recorded in the database. Subjects who met any of the criteria listed below will be treated as meeting the primary efficacy endpoint:

- 1) Death is recorded on the eCRF All Visits page “General Duration of Hospitalization, & Overall Requirement for Mechanical Ventilation, ICU Admission and/or Oxygen Supplementation”;
- 2) ICU admission date is recorded on the eCRF All Visits page “General Duration of Hospitalization, & Overall Requirement for Mechanical Ventilation, ICU Admission and/or Oxygen Supplementation”;
- 3) On the eCRF Day 29 page “Mechanical Ventilation and Oxygen Administration”:
  - a. subject on mechanical ventilation is recorded in the mechanical ventilation record for that day, i.e., “Is the subject on a ventilator?” is recorded as “Yes”;
  - Or
  - b. the modality of oxygen administration is recorded as “High flow oxygen devices”

If for a subject any of the 4 criteria above could not be assessed due to missing data, then the subject will be treated as meeting the endpoint in the primary efficacy analysis.

The null hypothesis is that there is no difference in the proportions of subjects who met the primary endpoint between randomized groups;  $H_0: \pi_t - \pi_c = 0$ . The alternative hypothesis is that the proportions of subjects who met the primary endpoint are different between the treatment groups;  $H_1: \pi_t - \pi_c \neq 0$ .

The proportion of subjects who met the criteria for the primary endpoint within each treatment group will be presented along with a two-sided exact (Clopper-Pearson) 95% confidence interval (CI).

The observed difference in the proportion of subjects meeting the criteria between treatment groups along with the exact unconditional 95% CI for risk difference will be calculated. The null hypothesis will be tested using Chi-square statistic and the p-value will be reported.

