## **6.3 Exploratory Efficacy Endpoints and Analyses**

- Change from baseline in quantitative SARS-CoV-2 viral load by NAT or PCR (RT-PCR) to Days 5±1, 15±1, and 29±1 will be summarized for each treatment group by visit.
- Change from baseline in quantitative anti- SARS-CoV-2 IgM and IgG antibodies to Days 5±1, 15±1, and 29±1 will be summarized for each treatment group by visit.
- The proportion of subjects with evidence of hyperinflammation on Days 1, 5, 15, and 29 will

be tabulated by treatment group. For this analysis, the denominator for calculating the proportion at each visit and within each treatment group will be the number of subjects with non-missing values for Lymphocyte counts AND for at least 2 of the following 4 lab parameters: Ferritin, LDH, D-Dimers, and C-reactive protein (i.e., the number of subjects for whom evidence of hyperinflammation could be assessed).

- Change from baseline in cytokine profile (IL-1 $\beta$ , IL-10, IL-6, IL-8 IL-2, interferon  $\gamma$ , and TNF- $\alpha$ ) to Days 5 $\pm$ 1, 15 $\pm$ 1, and 29 $\pm$ 1 will be summarized for each treatment group by visit.
- Change from baseline in levels of alpha 1-PI (AAT) activity and antigen to Days 8, 15, and 29 will be summarized for each treatment group by visit.

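### The hyperinflammation denominator admits lymphopenic subjects whose status is undetermined, and in effect counts them as not hyperinflamed

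*SAP*

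**What the plan says.** SAP 2.2.3, matching Protocol 7.1.3, defines the endpoint at Days 1, 5, 15 and 29 in two parts. The first is "Lymphocyte counts <1000 cells/µL, AND". The second is "Two of the following 4 criteria": ferritin, LDH, D-dimer and CRP, each against a cut-off.

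SAP 6.3 tabulates the proportion by treatment group, with no test. The denominator at each visit and in each arm is the subjects with a lymphocyte count and with values present "for at least 2 of the following 4 lab parameters". The SAP glosses this as "the number of subjects for whom evidence of hyperinflammation could be assessed".

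On missing data, SAP 4.4 says that, when applicable, "missing data for binary and selected continuous efficacy endpoints will be imputed using a most conservative/worst case approach", and adds that "the related details are described in Section 6". Section 6.3 contains no such details for this endpoint. Section 6.1 does contain them for the primary endpoint: if a component cannot be assessed, "then the subject will be treated as meeting the endpoint in the primary efficacy analysis".

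**The concern.** Two observed markers settle a two-of-four criterion only when both are raised. Take a lymphopenic subject with one raised marker, one normal marker and two missing. The missing values decide whether the definition is met, yet the rule calls the subject assessable. With no imputation in 6.3, the subject adds to the denominator and cannot add to the numerator.

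At stake is a descriptive proportion that serves a stated comparative exploratory objective (SAP 2.1.3). It would be understated by an amount that depends on how often single markers are missing. There is also an ambiguity for programming. The general worst-case sentence in 4.4, if applied here, would count the same subjects as positive, the opposite of what the 6.3 denominator implies.

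**Working it through.** The plan states no expected rate, sample size or power for this endpoint, so there is no figure to reproduce.

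**Step 1: which patterns are undetermined.** Each of the four markers can be raised, normal or missing. Among lymphopenic subjects the SAP 6.3 rule admits 72 marker patterns:

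| Markers observed | Patterns | Positive | Negative | Undetermined |
|---|---|---|---|---|
| 2 | 24 | 6 (2 of 2 raised) | 0 | 18 (0 or 1 of 2 raised) |
| 3 | 32 | 16 (2 or 3 raised) | 4 (0 of 3 raised) | 12 (1 of 3 raised) |
| 4 | 16 | 11 (2 or more raised) | 5 (0 or 1 raised) | 0 |

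So 18 + 12 = 30 of the 72 are undetermined. These are counts of patterns, not probabilities. Subjects with lymphocytes of 1000 or more are negative whatever the markers show, so the problem is confined to the 30.

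**Step 2: size on assumed inputs.** None of these inputs is in the documents: each marker raised with probability p = 0.5, markers independent, 50% of subjects lymphopenic, lymphocytes always available, each marker missing with probability m independently of its value and of the others.

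Given lymphopenia, the probability of at least two raised is 0.6875 with four markers observed, 0.500 with three and 0.250 with two. The true proportion is 0.5 × 0.6875 = 34.4%. The probability of being undetermined is 0.375 with three observed and 0.750 with two.

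For m = 0.10, the probabilities of observing 4, 3 and 2 markers are 0.6561, 0.2916 and 0.0486.

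- Denominator: 0.6561 + 0.2916 + 0.0486 = 0.9963.
- Numerator: 0.5 × (0.6561 × 0.6875 + 0.2916 × 0.5 + 0.0486 × 0.25) = 0.3045.
- Undetermined: 0.5 × (0.2916 × 0.375 + 0.0486 × 0.75) = 0.0729, or 7.3% of the denominator.
- SAP rule: 0.3045 / 0.9963 = 30.6%.
- Undetermined removed: 0.3045 / (0.9963 − 0.0729) = 33.0%.
- Undetermined all counted positive: (0.3045 + 0.0729) / 0.9963 = 37.9%.

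The same formulas over a range of m:

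| Missing per marker | SAP rule (= lower bound) | Undetermined removed | All four markers only | Upper bound |
|---|---|---|---|---|
| 2% | 33.6% | 34.1% | 34.4% | 35.1% |
| 5% | 32.5% | 33.7% | 34.4% | 36.2% |
| 10% | 30.6% | 33.0% | 34.4% | 37.9% |
| 20% | 27.0% | 31.3% | 34.4% | 40.8% |
| 30% | 23.8% | 29.5% | 34.4% | 43.1% |

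The share of subjects kept by the all-four table is (1 − m)^4: 92%, 81%, 66%, 41% and 24% down the rows.

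**Step 3: varying the other inputs.** Suppose a share s of subjects has exactly two markers and the rest have all four, with a lymphopenic share q. The understatement is q × s × (P4 − p²), where P4 is the probability of at least two raised among four. For p = 0.3, 0.5 and 0.7, P4 is 0.348, 0.688 and 0.916. With q from 0.4 to 0.6 and s from 0.1 to 0.3, it runs from 0.4 × 0.1 × (0.348 − 0.090) = 1.0 point to 0.6 × 0.3 × (0.688 − 0.250) = 7.9 points.

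**Step 4: whole panels missing.** If no single markers are missing but a share w of subjects lacks the whole panel, the SAP rule excludes those subjects and reports 34.4%, which is correct. Adding back only those with lymphocytes of 1000 or more gives (1 − w) × 0.344 / ((1 − w) + 0.5w): 32.6% at w = 0.10 and 30.6% at w = 0.20. That step would introduce a bias that the SAP rule does not have.

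**The case against.** The strongest reply is that partial panels may be rare. Protocol 7.2.3 makes ferritin, D-dimer, CRP and chemistry (which includes LDH) mandatory at Day 5 and drawn on one day. Sections 7.2.5 and 7.2.7 list the same tests for all subjects at Days 15 and 29, and Table 7-1 places them all at the local laboratory. A missed visit would lose the whole panel, which the SAP rule already handles properly. This stands as a limit on size. It does not exclude partial panels: the markers are separate tests, and Protocol 7.2.2 takes D-dimer from a citrate plasma tube but ferritin and CRP from serum.

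It can also be said that the endpoint concerns evidence of hyperinflammation, that two observed markers is the least that can show such evidence, and that the rule is stated in advance. That is a recognisable convention, but the SAP describes its denominator as those who could be assessed, and some of them could not.

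Three stronger readings are tempting and not supported:

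- A reader might infer that the SAP states that undetermined subjects are negative. It does not; this follows from the denominator rule together with the absence of any imputation in 6.3, and SAP 4.4 could be read the other way.
- A reader might infer a biased comparison between arms. The trial is double-blind with one laboratory schedule, and nothing in the documents suggests that missingness differs by arm.
- A reader might note that subjects with lymphocytes of 1000 or more and fewer than two markers are certain negatives, and want them added. The matching lymphopenic subjects would stay excluded, so adding them pulls the proportion down (Step 4).

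**Conclusion.** The point holds. The 6.3 denominator includes subjects whose status the two-of-four definition leaves open. Because the worst-case handling in 4.4 is not carried into 6.3, they are in effect scored not hyperinflamed, and the proportion is biased down when panels are partial.

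The size cannot be known from the documents. On the Step 2 assumptions the shortfall is under 1 point at 2% missing per marker, just under 2 points at 5%, about 4 points at 10% and between 10 and 11 points at 30%. It is nil if markers go missing only as whole panels. The consequence is small: the table is exploratory and untested, and the endpoint is not among those listed for the interim futility analysis in SAP 8.2.

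**What to change.** Amend the derivation in SAP 6.3 in one of two ways, chosen before unblinding:

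- Keep the existing denominator but remove subjects whose status is undetermined: lymphopenic, fewer than two markers observed raised, and enough missing for two to be possible.
- Or base the main table on subjects with lymphocytes and all four markers.

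Do not add subjects with lymphocytes of 1000 or more and fewer than two markers. State that the general worst-case sentence in 4.4 does not govern the main table. Report the number undetermined by arm and visit, with bounds that count them all as negative and all as positive.

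Neither option is a complete cure. Removing undetermined subjects is closer to the truth at every level in Step 2 but still low (29.5% against 34.4% at 30% missing), because those removed are all lymphopenic. The all-four table is unbiased only if markers are missing at random, unrelated to the results, and it keeps fewer subjects (66% at 10% missing per marker, 24% at 30%). The bounds show the reader how much this matters.

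The cost is one derivation rule and a few table rows, with no new data and no protocol change.

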## 7. SAFETY ANALYSIS

Safety assessments will include assessment of AEs, chemistry, hematology (complete blood count and differential), COVID-19 clinical features, vital signs, and hospital interventions. All safety summaries (or analyses if applicable) will be conducted using the SAF population. No formal hypothesis testing will be performed to compare differences between treatment groups.

### 7.1 Extent of Exposure and Compliance

The number of doses received, duration of infusion in minutes, infusion rate, the occurrence of dose interruption, whether 100% of study drug infused, total volume prepared, and total volume infused will be summarized by treatment group. In addition, treatment compliance will be calculated and summarized by treatment group. The summaries will include descriptive statistics of the treatment compliance as well as number and percentage of subjects with compliance between 80% and 120%.

Treatment compliance (%) will be calculated as follows:

$$\frac{\text{(Total volume infused over all infusions [mL]}}}{\text{Total volume prepared over all infusions [mL]}} \times 100.$$

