4.4.1.1 Liquid Alpha₁-PI (Human)

Liquid Alpha₁-PI (Human) has a nominal concentration of Alpha₁-Proteinase Inhibitor of 50 mg/mL. For a subject weighing 75 kg each dose of 120 mg/kg (on Day 1 and Day 8) would require 180 mL of Liquid Alpha₁-PI (Human) to achieve the specified 120 mg/kg dose.

Prior to administration, visually inspect parenteral drug products for particulate matter and discoloration. The product may contain a few protein particles. The solution is clear, colorless or pale yellow or pale green. Do not use if discolored or cloudy. Before delivery to the subject, Liquid Alpha₁-PI (Human) should be brought to room temperature and administered at room temperature for comfort to the subject. Liquid Alpha₁-PI (Human) is for IV administration only. Pooled Liquid Alpha₁-PI (Human) solution should be maintained at room temperature for administration within 3 hours.

Filter the solution during administration using an IV administration set with a suitable 5 to 15-micron infusion filter (not supplied). Infuse Liquid Alpha₁-PI (Human) separately, without mixing with other agents or diluting solutions. Infuse Liquid Alpha₁-PI (Human) IV at 0.08 mL/kg/min as determined by subject response and comfort. The Liquid Alpha₁-PI (Human) infusion line can be flushed with 0.9% sodium chloride for injection. Do Not flush with heparin.

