### 3. INVESTIGATIONAL PLAN

#### 3.1 Study Design

This is a prospective, multi-center, randomized, double-blind, placebo-controlled study of Liquid Alpha1-PI (Human) plus SMT versus placebo plus SMT in subjects with COVID-19 who are hospitalized. The first 6 subjects randomized will be staggered with an interval of no less than 1 week between subjects. If there are no definitely related SAEs reported by the time Day 8 is completed by the 6th subject, competitive enrollment would ensue thereafter. If a definitely related SAE were to be reported among these 6 subjects, and the subject was found by the Study-Independent Safety Review Committee (SISRC) to be randomized to the Liquid Alpha1-PI (Human) plus SMT arm, the SISRC would carefully review and evaluate the case and make appropriate recommendations with regard to study status.

In this study, symptomatic subjects with positive PCR (RT-PCR), NAT for SARS-CoV-2 (or other commercial or public health assay approved by regulatory authorities) will receive placebo plus SMT or SMT plus Liquid Alpha1-PI (Human) given as two intravenous (IV) doses of 120 mg/kg (body weight) one week apart (on Day 1 and Day 8); if the subject is discharged from the hospital then the 2nd infusion is not mandatory, and is at the discretion of the Principal Investigator (PI) and subject.

[figure not shown]
Specifically, subjects randomized to combination Liquid Alpha1-PI (Human) will receive the first IV infusion of blinded Liquid Alpha1-PI (Human) (120 mg/kg body weight) or Placebo on Day 1. A second Placebo/ Liquid Alpha1-PI (Human) dose of 120 mg/kg body weight will be administered a week later on Day 8. if the subject has been discharged from the hospital at the time of the Day 8 blinded Placebo/ Liquid Alpha1-PI (Human) infusion, the 2nd infusion is not mandatory, and is at the discretion of the PI and subject.

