### 3.2.3 Dosing Schedule

During this clinical trial, subjects randomized to receive combination Liquid Alpha1-PI (Human) plus SMT will receive the first dose of blinded Liquid Alpha1-PI (Human) given as an IV dose of 120 mg/kg (body weight) on Day 1. A second dose of blinded Liquid Alpha1-PI (Human) (120 mg/kg) will be infused on Day 8. If the subject has been discharged from the hospital at the time of the Day 8 blinded Liquid Alpha1-PI (Human) infusion, the 2nd infusion is not mandatory, and is at the discretion of the PI and subject.

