### 3.2.4 Treatment Compliance

Reasons for any deviation from the administration of less than 100% of the investigational product (IP) dose must be recorded in the subject's medical records.

The investigator or designee is responsible for maintaining accurate records of study medication administered at his/her study center.

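### Compliance is volume infused over volume prepared, so a Day 8 infusion that was due but never prepared, or a mis-filled bag, can score 100%

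*SAP*

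**What the plan says.** SAP 7.1 takes "Total volume infused over all infusions [mL", divides it by "Total volume prepared over all infusions [mL" and multiplies by 100. It then reports descriptive statistics of this percentage and the "number and percentage of subjects with compliance between 80% and 120" per cent. The same section also summarises by treatment group "The number of doses received, duration of infusion in minutes, infusion rate, the occurrence of dose interruption, whether 100% of study drug infused", together with the prepared and infused volumes.

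The regimen against which compliance would be judged is stated elsewhere. SAP 3.1 has the active product "given as two intravenous (IV) doses of 120 mg/kg (body weight) one week apart (on Day 1 and Day 8". Under SAP 3.2.3, once a subject has been discharged, the second "infusion is not mandatory, and is at the discretion of the PI and subject". Protocol 4.4.1.1 says the product "has a nominal concentration of Alpha₁-Proteinase Inhibitor of 50 mg/mL" and works out 180 mL per dose for a 75 kg subject. Placebo is made up to the matching volume (Protocol 4.4.1.2).

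SAP 3.2.4 asks sites to record "Reasons for any deviation from the administration of less than 100% of the investigational product (IP) dose". The reference there is the dose, not the volume in the bag.

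SAP 4.2 and Protocol 9.1 admit a subject to the per-protocol (PP) population only if 80% or more of the product was completed. Neither states the denominator, and neither refers to SAP 7.1.

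**The concern.** A compliance percentage should show how much of the intended treatment a subject received. Here the denominator is what the pharmacy made up. A Day 8 dose that was due but never prepared drops out of both numerator and denominator. A bag filled to the wrong volume and fully infused cancels in the same way. In both situations the subject is shown as fully compliant.

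The reporting band points to the same mismatch. A limit of 120% has a use only if the denominator is a planned amount that can be exceeded.

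At stake are each subject's reported compliance, the count of subjects within 80–120%, and possibly PP membership. The last matters because SAP 6.1 repeats the primary analysis on the PP population when it differs from the ITT population.

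**Working it through.** **Inputs.** Dose 120 mg/kg on Day 1 and Day 8 (SAP 3.1); nominal concentration 50 mg/mL and the 75 kg example (Protocol 4.4.1.1); compliance formula and 80–120% band (SAP 7.1); Day 8 optional only after discharge (SAP 3.2.3). The fill levels and infused fractions below are assumptions chosen for illustration; the documents give none.

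**The plan's own figure.** 75 × 120 / 50 = 180 mL per dose, which reproduces the protocol's 180 mL. Two doses make 2 × 180 = 360 mL.

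**Formulas.** SAP compliance = 100 × infused / prepared. Comparison = 100 × infused / planned, with planned = 360 mL for a subject still in hospital on Day 8.

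| Case (75 kg, both doses due) | SAP formula | Against planned volume |
|---|---|---|
| Both bags full and fully infused | 360/360 = 100% | 360/360 = 100% |
| Day 1 fully infused, no Day 8 bag prepared | 180/180 = 100% | 180/360 = 50% |
| Both bags half-filled, fully infused | 180/180 = 100% | 180/360 = 50% |
| Only the Day 8 bag half-filled, all infused | 270/270 = 100% | 270/360 = 75% |
| Both bags filled to 120%, fully infused | 432/432 = 100% | 432/360 = 120% |
| Day 1 bag 80% infused, no Day 8 bag | 144/180 = 80% | 144/360 = 40% |
| Day 1 bag 70% infused, no Day 8 bag | 126/180 = 70% | 126/360 = 35% |
| Day 8 bag prepared and counted, not infused | 180/360 = 50% | 180/360 = 50% |

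The last row shows that the formula does register a prepared but unused bag, provided it is counted. The SAP does not say whether it is. The two rows above it show that an incomplete Day 1 infusion lowers the score, but the unprepared Day 8 dose is still ignored: a subject given 40% of the planned volume sits on the 80% boundary.

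**Upper bound.** Barring recording error, infused volume cannot exceed prepared volume, so the ratio is at most 100% and the 120% limit is never reached.

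**Discharged subject who skips Day 8.** Only the Day 1 volume is due, so infused over due is 180/180 = 100%, the same as the SAP formula.

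**Is the no-bag case realistic?** Protocol 4.4.1.1 limits pooled product to 3 hours at room temperature, so a Day 8 bag would normally be made up only when the infusion is going ahead. Protocol 6.1 also rules out further infusions after a hypersensitivity reaction, and Protocol 5.3.2 provides for withdrawal; either can leave Day 8 unprepared.

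**The case against.** The strongest defence is that SAP 7.1 already reports the number of doses, whether the full amount was infused, and both volumes. A missed Day 8 dose is therefore visible in the dose count, and sites must record the reason for giving less than the full dose. This stands at group level. It does not correct the individual percentage or the 80–120% count.

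A reader might infer that compliance will come out near 100% whatever is given. The documents do not support that: an infusion stopped early scores below 100%, and so does an unused bag that is counted. A reader might also infer that every absent Day 8 dose is concealed non-compliance. It is not, because the dose is optional after discharge.

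Nor do the documents establish that the PP rule uses this formula. SAP 4.2 does not cite section 7.1. Major deviations are a separate ground for exclusion, and membership is assessed in a blinded review, where a missed mandatory dose could be caught. The PP effect is a risk, not a certainty.

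Mis-filling is hypothetical. An unblinded pharmacist or designee prepares the weight-based volume, and nothing in the documents suggests errors. The unreachable 120% limit changes no classification by itself; it only shows that band and formula do not match. Finally, 50 mg/mL is a nominal concentration, so a planned volume based on it is nominal too.

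**Conclusion.** The point holds in limited form. The SAP formula gives a misleading figure when a Day 8 infusion was due and no bag was prepared, or when a mis-filled bag was fully infused. For a subject in hospital on Day 8 with Day 1 fully infused, reported compliance is 100% against 50% of the planned volume. That ratio does not depend on body weight.

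How many subjects this affects is unknown, since the documents give no figure for missed Day 8 doses among those still in hospital. If the PP rule uses this formula, such a subject meets the 80% criterion on half the planned volume. The ITT primary analysis does not change. This is a minor but definite error of definition, worth correcting because the correction is cheap.

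**What to change.** In SAP 7.1, replace the denominator with the protocol-specified volume: baseline weight (kg) × 120 mg/kg ÷ 50 mg/mL (nominal), summed over the infusions due for that subject, with the matching volume for placebo. Then:

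- State that Day 8 is not counted as due after discharge. If a discharged subject does receive it, add its planned volume to the denominator; otherwise the figure becomes 360/180 = 200%.
- State how Day 8 is counted after death, withdrawal or a protocol-required stop of infusions. The documents are silent on this and the sponsor has to choose.
- Tie the PP 80% criterion in SAP 4.2 to the same definition, before the blinded population review.

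The 80–120% band can then stay, because its upper limit becomes reachable. No new data are needed: weight is recorded at Screening/Baseline and infused volume is already summarised. The cost is SAP wording, slightly more derivation work, and a compliance figure that may look less favourable.
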